**Table 7.1.3-1 Laboratory Tests**

Hematology	Chemistry	Urinalysis	Other
Hematocrit	Albumin	Blood	Serum $\beta$ -human chorionic gonadotropin (hCG)†
Hemoglobin	Alkaline phosphatase	Glucose	( $\beta$ -hCG)†
Platelet count	Alanine aminotransferase (ALT)	Protein	PT (INR)
WBC (total and differential)	Aspartate aminotransferase (AST)	Specific gravity	aPTT
Red Blood Cell Count	Lactate dehydrogenase (LDH)	Microscopic exam ( If abnormal )	Free thyroxine (T4)
Absolute Neutrophil Count	Carbon Dioxide ‡	results are noted	Thyroid stimulating hormone (TSH)
Absolute Lymphocyte Count	Creatinine		†Serum pregnancy test
	Uric Acid		
	Calcium		
	Chloride		Blood for correlative studies (at sponsor's discretion)
	Glucose		
	Phosphorus		
	Potassium		
	Sodium		
	Magnesium		
	Total Bilirubin		
	Direct Bilirubin ( If total bilirubin is elevated above the upper limit of normal )		
	Total protein		
	Blood Urea Nitrogen		

† Perform on women of childbearing potential only.

‡ If considered standard of care in your region.

### 7.1.3.1 Pharmacokinetic/Pharmacodynamic Evaluations

#### 7.1.3.1.1 Blood Collection for Serum Pembrolizumab

Not applicable. No pembrolizumab pharmacokinetic sampling will be performed.

#### 7.1.3.1.2 Blood Collection for Anti-Pembrolizumab Antibodies

Not applicable. No pembrolizumab pharmacokinetic sampling will be performed.

### 7.1.4 Other Procedures

#### 7.1.4.1 Withdrawal/Discontinuation

When a subject discontinues/withdraws prior to trial completion, all applicable activities scheduled for the final trial visit should be performed at the time of discontinuation. Any adverse events which are present at the time of discontinuation/withdrawal should be followed in accordance with the safety requirements outlined in **Section 7.2 - Assessing and Recording Adverse Events**.

Subjects who a) attain a CR or b) complete 24 months of treatment with pembrolizumab may discontinue treatment with the option of restarting treatment if they meet the criteria specified in **Section 7.1.5.5**. After discontinuing treatment following assessment of CR, these subjects should return to the site for a Safety Follow-up Visit (described in **Section**

7.1.5.4.1) and then proceed to the Follow-Up Period of the study (described in **Section 7.1.5.6**).

#### 7.1.4.2 Blinding/Unblinding

Not applicable. This is an open-label study, neither the patients nor the treating physicians are blinded.

### 7.1.5 Visit Requirements

Visit requirements are outlined in Section 6.0 - Trial Flow Chart. Specific procedure-related details are provided above in Section 7.1 - Trial Procedures.

#### 7.1.5.1 Screening: Donor

Donor screening will commence upon signing ICF. Donor screening will consist of stool sampling and **FMT Recipient (or Donor) Laboratory Testing** (as delineated in **Appendix 2**). Once collected, donor sample will be treated as outlined in **Section 4.2.3.1**.

#### 7.1.5.2 Screening: Recipient

Screening will commence once screen-eligible patients are found to have PD on first restaging scan following 2 cycles of pembrolizumab (or nivolumab). Screening procedures are outlined in Section 6.1: Study Flow Chart. Screening procedures include: administrative procedures (particularly informed consent wherein patients are only considered enrolled **after** protocol-specific informed consent is signed), clinical assessments and laboratory assessments (particularly **Appendix 1: FMT Recipient (or Donor) Screening Questionnaire** and **Appendix 2: FMT Recipient (or Donor) Laboratory Testing**). There is a 4-week (day -28 to day -1) window during which screening will take place.

#### 7.1.5.3 Treatment Period

Treatment period will commence once eligible patients have signed informed consent and have completed all administrative procedures including clinical assessments and laboratory assessments as outlined above and have been deemed eligible by Principal Investigator.

Treatment period will commence with colonoscopic administration of FMT by gastroenterologists. Following FMT, pembrolizumab (cycle 1) will be administered. There is a 3-day window (+/- 3 days) for administration of pembrolizumab. Prior to restaging, 3 further cycles will be administered. Schedule of activities during each treatment visit will be as outlined in **Section 6.1: Study Flow Chart**.

Patients will be restaged after 4 cycles of pembrolizumab. Patients with stable or responding disease will continue to receive pembrolizumab for an additional 4 cycles. Patients with stable or responding disease will continue to be followed by study team until completion of cycle 8 pembrolizumab and 2nd restaging study. Pembrolizumab will be administered for up to 24 months, progression or response (as outlined in Section 5.8.). Patients who have an initial response but develop subsequent PD, a 2nd administration of FMT (same or different

donor) will be considered at the discretion of the investigator and sponsor if the study remains open (as outlined in section 7.1.5.4.).

#### **7.1.5.4 Post-Treatment Visits**

End of treatment (EOT) is defined as the visit where the decision is made to discontinue the participant from treatment. Evaluations will be performed prior to study discharge, or for participants who are prematurely discontinued, or participants who complete all scheduled cycles of therapy, the EOT visit will be the same as the last scheduled and completed on-treatment visit.

For participants who complete all scheduled cycles of therapy, the EOT visit will be the same as the last scheduled and completed on-treatment visit (eg, Cycle 9 Day 1) and the start of the safety follow-up period. For participants that do not complete all scheduled cycles of therapy, the EOT visit will be the most recent on-treatment visit (with all available safety and response data), does not need to be repeated and will be considered the start of the safety follow-up period.

##### **7.1.5.4.1 Safety Follow-Up Visit**

The mandatory Safety Follow-Up Visit should be conducted approximately 30 days (+/- 10 days) after the last dose of trial treatment or before the initiation of a new anti-cancer treatment, whichever comes first. All AEs that occur prior to the Safety Follow-Up Visit should be recorded. Subjects with an AE of Grade > 1 will be followed until the resolution of the AE to Grade 0-1 (or baseline) or until the beginning of a new anti-neoplastic therapy, whichever occurs first. SAEs that occur within 90 days of the end of treatment or before initiation of a new anti-cancer treatment should also be followed and recorded. Subjects who are eligible for retreatment with pembrolizumab (as described in Section 7.1.5.5) may have up to two safety follow-up visits, one after the Treatment Period and one after the Second Course Phase.

#### **7.1.5.5 Re-Treatment Following Initial Response**

Following initial FMT with cycle 1 pembrolizumab, all patients will continue to receive further cycles of pembrolizumab as outlined in Section 5.8 and undergo periodic tumor assessment(s) as outlined in Section 7.1.2.6.

Re-treatment with FMT in patients who initially respond (RECIST v1.1-defined response) may be allowed in selected participants with disease progression during the safety, response or survival follow-up period. Eligibility will be dependent upon participants having confirmed disease progression and will be considered on a case by case basis following discussion with Principal Investigator.

Participants who meeting criteria for retreatment will be required to re-consent to study. Patients will be treated with a second course of FMT along with pembrolizumab. No more than 2 (two) FMT treatments will be permitted. Participants entering retreatment will follow

the same treatment schedule as outlined in Section 6.1. Biopsy and correlative analyses requirements will follow same schedule as well.

#### **7.1.5.6 Follow-up Visits**

Subjects who discontinue trial treatment for a reason other than disease progression will move into the Follow-Up Phase and be treated per standard-of-care. Patients should be assessed every 12 weeks by radiologic imaging to monitor disease status. After 1 year, the imaging time point will occur every 12 weeks ( $\pm$  7 days). Every effort should be made to collect information regarding disease status until the start of new anti-neoplastic therapy, disease progression, death, end of the study or if the subject begins retreatment with pembrolizumab as detailed in Section 7.1.5.5. Information regarding post-study anti-neoplastic treatment will be collected if new treatment is initiated.

##### **7.1.5.6.1 Survival Follow-up**

Once a subject experiences confirmed disease progression or starts a new anti-cancer therapy, the subject moves into the survival follow-up phase and should be followed every 12 weeks to assess for survival status until death, withdrawal of consent, or the end of the study, whichever occurs first.

#### **7.1.5.7 Second Course Phase**

Subjects who stop pembrolizumab with SD or better may be eligible for up to one year of additional pembrolizumab therapy if they progress after stopping study treatment. This retreatment is termed the Second Course Phase of this study and is only available if the study remains open and the subject meets the following conditions:

**1. Either**

- a. Stopped initial treatment with pembrolizumab after attaining an investigator-determined confirmed CR according to RECIST 1.1, and
  - i. Was treated for at least 24 weeks with pembrolizumab before discontinuing therapy
  - ii. Received at least two treatments with pembrolizumab beyond the date when the initial CR was declared

**OR**

- b. Had SD, PR or CR and stopped pembrolizumab treatment after 24 months for reasons other than disease progression or intolerability.

**AND**

2. Experienced an investigator-determined confirmed radiographic disease progression after stopping their initial treatment with pembrolizumab

3. Did not receive any anti-cancer treatment since the last dose of pembrolizumab
4. Has a performance status of 0 or 1 on the ECOG Performance Scale
5. Demonstrates adequate organ function as detailed in Section 5.1.2
6. Female subject of childbearing potential should have a negative serum or urine pregnancy test within 72 hours prior to receiving retreatment with study medication.
7. Female subject of childbearing potential should be willing to use 2 methods of birth control or be surgically sterile, or abstain from heterosexual activity for the course of the study through 120 days after the last dose of study medication (Reference Section 5.7.2). Subjects of child bearing potential are those who have not been surgically sterilized or have been free from menses for > 1 year.
8. Male subject should agree to use an adequate method of contraception starting with the first dose of study therapy through 120 days after the last dose of study therapy.
9. Does not have a history or current evidence of any condition, therapy, or laboratory abnormality that might interfere with the subject's participation for the full duration of the trial or is not in the best interest of the subject to participate, in the opinion of the treating investigator.

Subjects who restart treatment will be retreated at the same dose and dose interval as when they last received pembrolizumab. Treatment will be administered for up to one additional year.

Visit requirements are outlined in **Section 6.0 – Trial Flow Chart**.

## **7.2 Assessing and Recording Adverse Events**

An adverse event is defined as any untoward medical occurrence in a patient or clinical investigation subject administered a pharmaceutical product and which does not necessarily have to have a causal relationship with this treatment. An adverse event can therefore be any unfavorable and unintended sign (including an abnormal laboratory finding, for example), symptom, or disease temporally associated with the use of a medicinal product or protocol-specified procedure, whether or not considered related to the medicinal product or protocol-specified procedure. Any worsening (i.e., any clinically significant adverse change in frequency and/or intensity) of a preexisting condition that is temporally associated with the use pembrolizumab and/or FMT is also an adverse event.

Changes resulting from normal growth and development that do not vary significantly in frequency or severity from expected levels are not to be considered adverse events. Examples of this may include, but are not limited to, teething, typical crying in infants and children and onset of menses or menopause occurring at a physiologically appropriate time.

Adverse events may occur any time during the course of the clinical trial. Progression of the cancer under study is not considered an adverse event.

All adverse events that occur after the consent form is signed but before treatment initiation must be reported by the investigator if they cause the subject to be excluded from the trial, or are the result of a protocol-specified intervention, including but not limited to washout or discontinuation of usual therapy, diet, placebo treatment or a procedure.

From the time of treatment initiation through 30 days following cessation of treatment, all adverse events must be reported by the investigator. Such events will be recorded at each examination on the Adverse Event case report forms/worksheets. The reporting timeframe for adverse events meeting any serious criteria is described in section 7.2.3.1. The investigator will make every attempt to follow all subjects with non-serious adverse events for outcome.

Adverse events will not be collected for subjects during the screening period as long as that subject has not undergone any protocol-specified procedure or intervention. If the subject requires a blood draw, fresh tumor biopsy etc., the subject is first required to provide consent to the main study and AEs will be captured according to guidelines for standard AE reporting.

### **7.2.1 Definition of an Overdose for This Protocol and Reporting of Overdose to the Sponsor and to Merck**

For purposes of this study, reporting of adverse events will commence after administration of study agents (day +1 and onwards). Adverse events occurring prior to this including those during pre-screening period, screening period and during prior pembrolizumab (or nivolumab) administration will be captured as part of the medical record but will not be submitted.

For purposes of this trial, an overdose of pembrolizumab will be defined as any dose of 1,000 mg or greater ( $\geq 5$  times the indicated dose); while an overdose of FMT will be defined as any dose exceeding 3 administrations at a given time (dose  $\geq 3$  times the indicated dose). No specific information is available on the treatment of overdose of pembrolizumab. No specific information is available on the treatment of overdose of FMT. Appropriate supportive treatment should be provided if clinically indicated. In the event of overdose, the subject should be observed closely for signs of toxicity. Appropriate supportive treatment should be provided if clinically indicated.

If an adverse event(s) is associated with (“results from”) pembrolizumab and/or FMT, the adverse event(s) is reported as a serious adverse event, even if no other seriousness criteria are met.

If a dose of pembrolizumab and/or FMT meeting the protocol definition of overdose is taken without any associated clinical symptoms or abnormal laboratory results, the overdose is reported as a non-serious Event of Clinical Interest (ECI), using the terminology “accidental or intentional overdose without adverse effect.”

All reports of overdose with and without an adverse event must be reported within 24 hours to the Sponsor and within 2 working days hours to Merck Global Safety. (Attn: Worldwide Product Safety; [contact]).

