## 4.2.4 Rationale for Endpoints

### 4.2.4.1 Efficacy Endpoints

Primary efficacy endpoint: safety/toxicity and objective response rate (ORR) by RECIST 1.1.

Secondary efficacy endpoints: include incidence of grade III/IV toxicities, safety of FMT administration endoscopically, progression-free survival (PFS), and overall survival (OS).

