## **7.2.3 Immediate Reporting of Adverse Events to the Sponsor and to Merck**

### **7.2.3.1 Serious Adverse Events**

An SAE is any AE that fulfills one of the criteria outlined in **Table 6**.

Examples of such "important medical events" include allergic bronchospasm requiring intensive treatment in an emergency room or at home, blood dyscrasias or convulsions that do not result in inpatient hospitalization, or the development of drug dependency or drug abuse.

Medical and scientific judgment should be exercised in deciding whether expedited reporting is appropriate in other situations, such as with important medical events described above.

Events that meet SAE criteria must be recorded and reported regardless of expectedness or assessed association with study drug.

**Note:** Planned hospital admissions or surgical procedures for elective procedures or for an illness or disease that existed before the signing of the ICF or before the subject was enrolled in the study will not be captured as SAEs. If planned admissions or procedures occur at a

time other than what was planned (i.e., due to an exacerbation in the preexisting illness or disease), they should be reported as SAEs.

For the time period beginning when study drugs (FMT and pembrolizumab combination on day +1) are administered, any serious adverse event, or follow up to a serious adverse event, including death due to any cause other than progression of the cancer under study (reference Section 7.2.3.3 for additional details) that occurs to any subject must be reported within 24 hours to the Principal Investigator and within 2 working days to Merck Global Safety if it causes the subject to be excluded from the trial, or is the result of a protocol-specified intervention, including but not limited to washout or discontinuation of usual therapy, diet, placebo treatment or a procedure.

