### **7.2.4 Evaluating Adverse Events**

An investigator who is a qualified physician will evaluate all adverse events according to the NCI Common Terminology for Adverse Events (CTCAE), version 5.0. Any adverse event which changes CTCAE grade over the course of a given episode will have each change of grade recorded on the adverse event case report forms/worksheets.

All adverse events regardless of CTCAE grade must also be evaluated for seriousness and attribution to pembrolizumab and/or FMT.

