	Is an overdose (whether accidental or intentional). Any adverse event associated with an overdose is considered a serious adverse event for collection purposes. An overdose that is not associated with an adverse event is considered a non-serious event of clinical interest and must be reported within 24 hours to the Sponsor and to Merck within 2 working days..	
Other important medical events that may not result in death, not be life threatening, or not require hospitalization may be considered a serious adverse event when, based upon appropriate medical judgment, the event may jeopardize the subject and may require medical or surgical intervention to prevent one of the outcomes		

	listed previously (designated above by a †).	
Duration	Record the start and stop dates of the adverse event. If less than 1 day, indicate the appropriate length of time and units	
Action taken	Did the adverse event cause pembrolizumab and/or FMT to be discontinued?	
Relationship to pembrolizumab	Did pembrolizumab and/or FMT cause the adverse event? The determination of the likelihood that pembrolizumab and/or FMT caused the adverse event will be provided by an investigator who is a qualified physician. The investigator's signed/dated initials on the source document or worksheet that supports the causality noted on the AE form, ensures that a medically qualified assessment of causality was done. This initialed document must be retained for the required regulatory time frame. The criteria below are intended as reference guidelines to assist the investigator in assessing the likelihood of a relationship between the test drug and the adverse event based upon the available information.  The following components are to be used to assess the relationship between pembrolizumab and/or FMT and the AE; the greater the correlation with the components and their respective elements (in number and/or intensity), the more likely pembrolizumab and/or FMT caused the adverse event (AE):	
	Exposure	Is there evidence that the subject was actually exposed to pembrolizumab and/or FMT such as: reliable history, acceptable compliance assessment (pill count, diary, etc.), expected pharmacologic effect, or measurement of drug/metabolite in bodily specimen?

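### Section 7.2.1 has two reporting rules, on seriousness and on when adverse event reporting starts, that contradict the rest of the protocol's safety text

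*Combined protocol and SAP*

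**What the plan says.** **Seriousness.** Section 7.2.1 takes an adverse event that results from pembrolizumab and/or FMT and states that "the adverse event(s) is reported as a serious adverse event, even if no other seriousness criteria are met". The sentence does not mention overdose. Three other places differ:

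- Table 7.2.4-1: "Any adverse event associated with an overdose is considered a serious adverse event for collection purposes".
- Section 7.2.3.1: "An SAE is any AE that fulfills one of the criteria outlined in" a table of criteria. The criteria printed in Table 7.2.4-1 do not include relatedness.
- Section 7.2.4: "All adverse events regardless of CTCAE grade must also be evaluated for seriousness and attribution to pembrolizumab and/or FMT".

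**Start of reporting.** The first paragraph of Section 7.2.1 says that "reporting of adverse events will commence after administration of study agents (day +1 and onwards"). Earlier events, including those in screening, go into the medical record and are not submitted. Section 7.2 says: "All adverse events that occur after the consent form is signed but before treatment initiation must be reported by the investigator", on condition that they lead to exclusion or result from a protocol-specified intervention or procedure. For a patient who needs a blood draw or fresh biopsy, it adds that consent comes first and "AEs will be captured according to guidelines for standard AE reporting".

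**Endpoints.** Section 4.2.4.1 lists safety/toxicity with ORR as primary, and names "safety of FMT administration endoscopically" among the secondary endpoints.

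**The concern.** An investigator who follows Section 7.2.1 and one who follows Section 7.2 with Table 7.2.4-1 would file different reports for the same event.

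On seriousness, a mild event judged to result from treatment is an SAE under one text and not under the other. SAEs go to the Principal Investigator within 24 hours and to the drug manufacturer within 2 working days (Section 7.2.3.1). The IRB filter in Section 10.5 uses seriousness as one of three tests, with relatedness and unexpectedness. The DSMB reviews SAEs, and the DSMC progress reports summarise them. If every related event is serious, these channels lose the distinction they rely on.

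On timing, a complication of a procedure done only because of the protocol is both reportable and not to be submitted. In a trial with safety in its primary endpoint, the procedural burden before dosing should not depend on which paragraph the site reads.

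**Working it through.** The documents give no SAE or pre-dose event counts or rates, so there is no figure to reproduce. The check is a comparison of texts, followed by tracing each rule to where its output is used.

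**Step 1. Is the seriousness conflict real?** Take a grade 1 flatulence (an item on the Appendix 4 memory card), judged to result from FMT, with no overdose and no other criterion met.

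| Text | Classification |
|---|---|
| Section 7.2.1, literal | SAE |
| Table 7.2.4-1 | Not serious: no overdose, no listed criterion |
| Section 7.2.3.1 | Not serious: no listed criterion |
| Section 7.2.4 | Attribution does not settle seriousness |

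Section 7.2 also provides for follow-up of non-serious events, which presupposes that they exist. The conflict is real on the current wording.

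**Step 2. Where does seriousness enter?** For the same event:

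- Toxicity tables (Section 8.5.2) use maximum CTCAE grade. The event is grade 1 either way.
- The DLT rule (Section 8.3) needs grade 3 or greater within four weeks of FMT. It is unaffected.
- The stopping rule (Section 8.4) depends on a death at least possibly related within 30 days. It is unaffected.
- The ORR decision (Section 8.5.1.2) counts responses. It is unaffected.
- The secondary toxicity endpoint (Section 4.2.4.1) is incidence of grade III/IV events. It is unaffected.
- SAE counts, expedited reports (Section 7.2.3.1), and IRB reports and DSMB/DSMC review (Section 10.5) all take seriousness as an input. These are affected.

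**Step 3. Is the start-of-reporting conflict real?** Take a complication of the screening tumor biopsy, which Section 7.1.2.7 schedules on Day -21 to -1, in a consented patient.

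| Text | Handling |
|---|---|
| Section 7.2 | Reported, because it results from a protocol procedure |
| Section 7.2.1, first paragraph | Medical record only, not submitted |
| Section 7.2.3.1, if serious | Before the stated window, which opens when study drugs are given on day +1 |

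Section 7.2.3.1 shows the same tension internally. Its first reporting-window paragraph opens at day +1, yet limits reporting to events that cause exclusion or result from a protocol intervention. In Sections 7.2 and 7.2.3.2 that limit belongs to the period between consent and treatment.

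**Step 4. Which events fall in the gap?**

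- Screening biopsy: Section 11.1 requires it of all patients, before dosing.
- Bowel preparation: Section 5.1.1 requires it before the colonoscopy.
- Colonoscopy: Section 4.2.3 delivers the infusate through the endoscope, and Section 7.1.5.3 starts the treatment period with that administration. Events during or after infusion are therefore covered by the Section 7.2 rule that runs from treatment initiation. Only events in the same procedure before the infusate is given are exposed.

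**Step 5. Can pre-dose events simply join the toxicity tables?** Section 5.10 makes a patient evaluable for safety only after FMT and at least one pembrolizumab dose. A patient excluded before dosing is outside that set. Such events need their own listing.

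**The case against.** The best reply on seriousness is that a phrase was dropped. The sentence stands under an overdose heading, between the overdose definition and a paragraph on overdose without symptoms. Its reference to other seriousness criteria presupposes that one, overdose, has just been named. That account of its origin is very likely right. It does not cure the text: the next paragraph states the overdose condition in full, so a site could take its absence here as intended.

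On timing, Section 7.2.1 keeps pre-dose events in the medical record, and screening-biopsy complications say little about the safety of endoscopic FMT. Both points stand. They limit the consequence but leave two incompatible instructions.

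A reader might infer three stronger things that the documents do not support:

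- *The primary toxicity result is inflated.* No planned analysis counts SAEs; the tables use CTCAE grade.
- *Colonoscopy complications are dropped.* Most arise on or after treatment initiation and are reportable under Section 7.2.
- *All 20 patients would be affected.* That is the planned enrolment, and so a ceiling on exposure. It does not count misclassified or lost events.

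**Conclusion.** Both contradictions are in the current text and should be corrected. They are drafting inconsistencies in the reporting rules and do not show a flaw in the design.

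The seriousness sentence, read literally, affects SAE counts, expedited and IRB reports, and DSMB/DSMC review. It does not affect the grade-based toxicity tables, the DLT rule, the stopping rule or the ORR decision.

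The start rule may leave unsubmitted the complications of screening biopsy and bowel preparation, and the few colonoscopy events that precede infusion. They remain in the medical record.

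No size is given for either effect, because the documents supply no rates of related, serious or pre-dose events. The conclusion assumes that sites would apply Section 7.2.1 as written; a site working from Section 7.2 and Table 7.2.4-1 would report correctly.

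**What to change.** 1. In the seriousness sentence of Section 7.2.1, insert 'an overdose of' before 'pembrolizumab and/or FMT', so that it agrees with Table 7.2.4-1.
2. Replace the first paragraph of Section 7.2.1 with the Section 7.2 rule: from consent to first treatment, report events that cause exclusion or result from a protocol-specified procedure. Because that rule begins at consent, events during prior PD-1 therapy before consent stay out of scope.
3. Align the day +1 SAE start in Section 7.2.3.1 with that rule. Otherwise a serious biopsy complication would still fall outside the expedited window.
4. State in Section 8.5.2 that pre-dose procedure-related events are listed separately from the toxicity tables for treated patients, given the safety-evaluable definition in Section 5.10.

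The edits touch a few sentences in three sections, with slightly more pre-dose adverse event entry. Sample size, decision rules and the definition of evaluable patients do not change.
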